3.1.3 Exploratory Objective(s)

Eisai Final 4.0 Confidential Page 8 of 30

3.2 Overall Study Design and Plan

This is a multicenter, multiple-dose, randomized, double-blind, placebo-controlled, parallel-group adjunctive therapy study in subjects with Dravet syndrome. The study is planned to be conducted in US, Canada, India, and China or Brazil (to be determined). The study will consist of a Core Study and open-label Extension Phase.

The Core Study will include a Prerandomization and a Randomization Phase.

The Prerandomization Phase will include a Screening/Baseline Period (4 weeks), during which the subjects will be assessed for eligibility.

Once the Screening and Baseline procedures have been completed and eligibility has been established, the subjects will be randomized and begin treatment in the Randomization Phase. Approximately 62 subjects will be randomized to 1 of 2 treatment groups in a ratio of 1:1 and will receive lorcaserin or placebo for 14 weeks. The randomization will be centralized and stratified by previous treatment with fenfluramine (yes, no) and by weight categories (10 to <20 kg, 20 to <40 kg, and ≥40 kg). The stratification factors will be balanced between treatment groups using restricted randomization method proposed by Pocock and Simon (1975).

The Randomization Phase will consist of 2 periods: Treatment Period (14 weeks) and Follow-up Period (4 weeks).

During the Treatment Period, all subjects will take study drug twice daily (BID) based on weight category at randomization, as described in Section 9.4.1 of the protocol.

For lower weight categories, during the first 2 weeks of Treatment Period, the dose may be increased (not earlier than after 1 week of treatment) by 1 dose level at a visit. If the dose was increased, in the event of AEs, according to the investigator's clinical judgment, the dose may remain the same or can be decreased by 1 dose level, to the Target dose at any time during the Treatment Period. If the dose had been decreased, it may be increased again if tolerability improves.

All subjects who complete the Core Study will be eligible to enter the Extension Phase (refer to Appendix 2 of the protocol). The last visit of the Treatment Period of the Core Study is considered to be the 1st visit of the Extension Phase.

The Follow-up Visit will be conducted 4 weeks after the last dose of study drug for subjects who do not enter the Extension Phase.

Eisai Final 4.0 Confidential Page 9 of 30

dose

Phase: OLE Follow-Up* Prerandomization Randomization Treatment Screening/Baseline Treatment Period: E2023 E2023 OL R E2023 Placebo Core Study 4 weeks Week 0 Week 14 <4 weeks Week 26 after last

An overview of the study design is presented in Figure 1.

Figure 1 Study Design: E2023-A001-304 Core Study and Extension Phase

Follow-up can occur during the Randomization Phase (if the subject discontinued during the Randomization Phase), or during the Extension Phase, after the termination of study treatment.

*All subjects will have follow-up 4 weeks after the end of the treatment and a final assessment completed. OL = open-label, OLE = open-label extension, R = randomization.

4 DETERMINATION OF SAMPLE SIZE

A sample size of 54 subjects (27 per group) will have 90% power to detect a difference of 50% reduction in convulsive seizure frequency per 28 days between lorcaserin and placebo assuming a standard deviation of 55, using a 2-group t-test with 0.05 two sided significance level. This sample size will have 90% power to detect an odds-ratio of at least 10 for the secondary endpoint 50% reduction in convulsive seizure frequency, assuming the placebo response is 12%, using a 2-group Chi-square test with 0.05 two-sided significance level. Sample size was estimated based on the percent reduction of convulsive seizures and standard deviation reported in fenfluramine study in Dravet syndrome (Lagae et al., 2020). Approximately 62 subjects will be randomized assuming a dropout rate of 12%.

5 STATISTICAL METHODS

All statistical analyses will be performed by the sponsor or designee after the study is completed and the database is locked and released for unblinding and a snapshot of the

Eisai Final 4.0 Confidential Page 10 of 30

database is obtained and released for unblinding. Statistical analyses will be performed using SAS software or other validated statistical software as required.

All descriptive statistics for continuous variables will be reported using mean, standard deviation (SD), median, minimum and maximum. Categorical variables will be summarized as number (percentage) of subjects.

5.1 Study Endpoints

5.1.1 Primary Endpoint

 Percent change from baseline in seizure frequency of convulsive seizures during the Treatment Period

5.1.2 Key Secondary Endpoint

Proportion of 50% responders for convulsive seizures in the Treatment Period

5.1.3 Other Secondary Endpoints

- Proportion of subjects who are free from convulsive seizures in the Treatment Period
- PK parameters of lorcaserin in the Treatment Period
- Safety and tolerability, including incidence of treatment-emergent adverse events (TEAEs)

5.1.4 **Exploratory Endpoints**

5.2 Study Subjects

5.2.1 Definitions of Analysis Sets

The Safety Analysis Set is the group of subjects who received at least 1 dose of study drug and had at least 1 postdose safety assessment.

The Full Analysis Set is the group of randomized subjects who received at least 1 dose of

Eisai Final 4.0 Confidential Page 11 of 30 study drug and had at least 1 postdose primary efficacy measurement.

The PK Analysis Set is the group of all randomized subjects from whom at least measurable lorcaserin plasma concentration was obtained with associated documented dosing history.

5.2.2 Subject Disposition

The number of subjects screened and the number (percentage) of subjects who failed screening and the reasons for screen failure will be summarized, based on data reported on the CRF.

5.2.3 Protocol Deviations

Major protocol deviations will be summarized by number (percentage). In addition, a subject listing will be provided along with the description of the protocol deviation. Protocol deviations will be identified prior to database lock.

5.2.4 Demographic and Other Baseline Characteristics

Demographic and other baseline characteristics for the Full Analysis Set will be summarized using descriptive statistics. Continuous demographic and baseline variables include age, height, BMI, and weight; categorical variables include sex, race, and region.

MEDICAL HISTORY

The number (percentage) of subjects in the Full Analysis Set reporting a history of any medical condition, as recorded on the CRF, will be summarized for each treatment group and overall. A subject data listing of medical and surgical history will be provided.

5.2.5 Prior and Concomitant Therapy

All investigator terms for medications recorded in the CRF will be coded to an 11-digit code using the World Health Organization Drug Dictionary. The number (percentage) of subjects who took prior and concomitant medications will be summarized on the Full Analysis Set by Anatomical Therapeutic Chemical class and World Health Organization Drug Dictionary preferred term (PT). Prior medications will be defined as medications that stopped before the first dose of study drug. Concomitant medications will be defined as medications that (1) started before the first dose of study drug and were continuing at the time of the first dose of study drug, or (2) started on or after the date of the first dose of study drug up to the subject's last dose or 28 days after the subject's last dose for subjects who do not enter the extension phase (for core study analysis) or do not enter Study E2023-A001-405 (for extension phase analysis). All medications will be presented in subject data listings.

Eisai Final 4.0 Confidential Page 12 of 30

5.2.6 Treatment Compliance

Overall compliance rate will be determined and defined as the difference in the tablets dispensed minus the number of tables returned, divided by the expected number of tablets to be taken, multiplied by 100. Descriptive statistics (n, mean, standard deviation, median minimum, maximum) and number (percentage) of subjects in compliance categories (<50%, 50 to <80%, 80 to ≤120%, >120%) will be provided for the entire double-blind core phase. The Safety Analysis Set will be used.

5.3 Data Analysis General Considerations

5.3.1 Adjustments for Covariates

In the statistical models, the randomization stratification variables for fenfluramine (yes, no) and weight categories (10 to <20 kg, 20 to <40 kg, and ≥40 kg) will be included as covariates. Other covariates include region, baseline seizure frequency, and treatment-by-region interaction.

5.3.2 Multiple Comparisons/Multiplicity

In order to control for Type I error, a sequential gatekeeping approach will be used where the primary endpoint will be tested first at 0.05 level, if the null hypothesis is rejected, the key secondary endpoint will be tested at 0.05 significance level. Otherwise no further testing will be performed.

5.3.3 Examination of Subgroups

The primary endpoint and key secondary endpoint will be summarized using descriptive statistics by each subgroup listed below. No hypothesis testing will be performed in the subgroup analyses.

- Age group (≥ 2 to ≤ 12 yrs, ≥ 12 yrs)
- Sex (male and female)
- Race (white, black, Asian, and other)
- Region (US and Canada, India, and China/Brazil)
- Weight Strata (10 to \leq 20 kg, 20 to \leq 40 kg, and \geq 40 kg)
- Fenfluramine strata (yes, no)
- Prior to drug interruption, during drug interruption and after drug interruption
- Seizure types

Additional subgroup analyses may also be conducted, if deemed appropriate.

Eisai Final 4.0 Confidential Page 13 of 30

5.3.4 Handling of Missing Data, Dropouts, and Outliers

The primary efficacy endpoint, percent change from baseline in convulsive seizures, will be analyzed using rank ANCOVA model. Seizure frequency for convulsive seizures will be based on number of seizures per 28 days, calculated during the Baseline Period and Double-blind Treatment Period, as the number of seizures during each respective period divided by the number of non-missing days during each respective period, multiplied by 28. Additional sensitivity analysis will be performed using multiple imputation (MI) assuming missing not at random (MNAR) to impute missing weeks on the primary efficacy endpoint as follows:

Table 1 Multiple Imputation Method

MI Methods	Assumpt	tion							
Available Case Missing Value	This MI method will use all available monotone missing patterns to impute missing data assuming MNAR.								
	Visit	1	2	3	4	5	6	7	8
	Week	Screening	0	1	2	4	6	10	14
	Pattern								
	1	X	X	X	X	X	X	X	X
	2	X	X	X	X	X	X	X	
	3	X	X	X	X	X	X		
	4	X	X	X	X	X			
	5	X	X	X	X				
	6	X	X	X					
	7	X	X						
	8	X							
	X=obse	rved data; .	-missin	g data					

The MI algorithm is described in Section 5.4.1 and SAS pseudo program code is found Section 9.

5.3.5 Other Considerations

The following estimands are evaluated for the primary efficacy endpoint, percent change from baseline in seizure frequency per 28 days in convulsive seizures, and key secondary endpoint, 50% reduction of convulsive seizures per 28 days.

Eisai Final 4.0 Confidential Page 14 of 30

Table 2	Table 2 Estimands for Primary and Key Secondary Endpoints				
Estimand	Description	Population	Intervention Effect of Interest	Analysis Type	
Difference in outcomes	all randomized subjects regardless of the treatment subjects actually received; subjects with any observed data		Seizure frequency for convulsive seizures will be based on number of seizures per 28 days, calculated during the Baseline Period and Treatment Period, as the number of seizures during each respective period divided by the number of non-missing days during each respective period, multiplied by 28	Endpoint	
Difference in outcomes	all randomized subjects regardless of the treatment subjects actually received	FAS	har the hard	Endpoint	
Difference in outcomes	all randomized subjects regardless of the treatment subjects actually received		primary endpoint	Key Secondary Endpoint	
Difference in outcomes	all randomized subjects regardless of the treatment subjects actually received		data based on the sensitivity analysis of	Sensitivity to Key Secondary Endpoint	

5.4 Efficacy Analyses

Seizure frequency for convulsive seizures, total seizures, non-convulsive and per seizure, will be based on number of seizures per 28 days, calculated during the Baseline Period and Treatment Period, as the number of seizures during each respective period divided by the number of non-missing days during each respective period, multiplied by 28.

Eisai Final 4.0 Confidential Page 15 of 30

5.4.1 Primary Efficacy Analysis

Percent change from baseline in seizure frequency per 28 days for convulsive seizures will be analyzed using rank ANCOVA with treatment, fenfluramine, weight, and region strata, and treatment-by-region interaction as factors, and the baseline seizure frequency as a covariate. In this analysis, all seizure frequency data will be rank transformed first for both baseline period and treatment period seizure frequencies separately. The median percent change from baseline and the 95% confidence interval (CI) will be calculated within treatment groups and for comparison of treatment groups (lorcaserin vs. placebo).

Null Hypothesis: No difference exists in the percent mean change from Baseline in convulsive seizures of treatment with lorcaserin as compared with PBO.

Alternative Hypothesis: A difference exists in the percent mean change from Baseline in convulsive seizures for lorcaserin as compared with PBO.

5.4.1.1 Multiple Imputation

Prior to MI, seizure frequency will be log-tranformed in order to assume a multivariate log-normal distribution.

Step 1 (imputing missing data): Thirty multiple imputed complete datasets were to be constructed using imputation regression model of age, weight, day1 to day98 (or last day of double-blind phase) with a predefined arbitrary seed number (seed = 2023). The dataset will be converted into monotone missing pattern by imputing arbitrary missing data as the first step. The monotone data will then be imputed with monotone Fully Conditional Specification (FCS) predictive mean matching (PMM) regression method with neighbor size (k=5) and MNAR.

The thirty complete imputed datasets will be back transformed by exponentiation of the log-transformed data. The sample SAS statements can be found in Section 9.

Step 2 (performing rank ANCOVA using each imputed dataset): For each of the thirty imputed datasets the seizure frequency per 28 days for the Baseline Period and Treatment Period will be derived and the percent change from baseline will be determined. The rank ANCOVA model for the primary efficacy analysis will be used on each of the thirty imputed datasets. SAS PROC MIXED will be used. The sample SAS statement can be found in Section 9.

Step 3 (combine results): Resulting treatment effect parameter estimators and standard errors from each of 30 multiple imputed datasets from Step 2 will be combined using SAS PROC MIANALYZE to obtain the pooled treatment effect and variance parameter estimators according to Rubin's rules (Rubin DB, 1987). The sample SAS statement can be found in Section 9.

Eisai Final 4.0 Confidential Page 16 of 30

5.4.2 Key Secondary Efficacy Analysis

Proportions of subjects who experience a 50% or greater reduction in convulsive seizure frequency in the Treatment Period relative to the Baseline Period will be conducted based on Cochran-Mantel-Haenszel test and 95% CI, adjusted for fenfluramine, weight, and region strata.

5.4.3 Other Efficacy Analyses

No other efficacy analyses are planned for this study.

5.5 Pharmacokinetic, Pharmacodynamic, Pharmacogenomic, and Other Biomarker Analyses

Details of the analysis methods for population PK/PD modeling will not be described in this SAP but will be described in a separate analysis plan.

5.5.1 Pharmacokinetic Analyses

Analysis of PK will be performed on the PK Analysis Set. Plasma concentrations of lorcaserin will be listed.

Lorcaserin plasma concentration-time data will be subjected to population PK analysis using nonlinear mixed effects modeling. For this approach, PK analysis data from this study will be pooled with relevant data from other lorcaserin studies as appropriate. The effect of covariates, such as baseline characteristics/demographics, on PK will be explored. Derived exposure parameters such as C_{max} and AUC at steady-state will be calculated from the final PK model using individual posterior estimates of the PK parameters and from dosing history.

Relationships between exposure to lorcaserin and selected efficacy and safety endpoints will be explored graphically if data permits. Any emergent PK/pharmacodynamic relationship will be followed by population PK/pharmacodynamic modeling if data allow.

5.5.2 Pharmacodynamic, Pharmacogenomic, and Other Biomarker Analyses

Data may be analyzed based on types of genetic mutations related to epilepsy.

5.6 Safety Analyses

Safety analyses will be conducted on the Safety Analysis Set. The data will be summarized by overall, treatment group, using descriptive statistics (eg, n, mean, standard deviation, median, minimum, maximum for continuous variables; n [percentage] for categorical variables).

The incidence of TEAEs, SAEs, AEs leading to discontinuation of study drug, and AEs leading to dose adjustment will be summarized. The incidence of TEAEs will be summarized by severity (mild, moderate, or severe), as well as by relationship to treatment (related or not

Eisai Final 4.0 Confidential Page 17 of 30

related). Proportion of subjects with increased seizure frequency, weight and BMI changes will be summarized.

The change from baseline in vital signs and ECG parameters will be summarized, and changes from baseline in laboratory values will be summarized for continuous variables.

Incidence of FDA-defined valvulopathy, pulmonary hypertension, and change from baseline of echocardiographic parameters will be summarized. Incidence of bradycardia, new onset heart block, new onset of other arrhythmias or conduction abnormalities, thickened valve leaflets, and restricted valve leaflet motion will be summarized.

Proportion of subjects with any treatment-emergent study-specific AEs will be summarized.

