7.2 Clinical Experience

Tolete et. al (2018) summarize a retrospective chart review (Jan 2014 – Jan 2018) of 36 patients with childhood-onset refractory epilepsies (Dravet syndrome [20 patients], Lennox-Gastaut syndrome [9 patients], other treatment-resistant focal epilepsies [3 patients], and generalized epilepsies [3 patients]) administered lorcaserin. Thirty-three (94.3%) patients were taking at least 1 antiseizure medication (mean = 3; clobazam [60%], valproic acid [57.1%], and cannabidiol [40%]). Of the 35 patients analyzed, the median percentage reduction from baseline in the mean monthly frequency of motor seizures was 47.7% ($z=-3.04$, $P<0.01$; 46.9% in tonic-clonic, 62.3% in tonic, 60.1% in atonic, and 54.6% in focal seizures with motor features); 15 (42%) had greater than 50% reduction in motor seizures. Two (5.7%) patients had increased seizure frequency. The mean lorcaserin dosage was 15.7 mg/d (and 13.7 mg/d for children) and median treatment duration was 10.8 months. After 15 months, 50% of patients remained on lorcaserin. The most common AEs reported were decreased appetite (19.6%), decreased attentiveness (17.1%), and weight loss (11.1%). The mean decline in body mass index (BMI) at last follow-up compared to baseline was $-0.58 \pm 0.24 \text{ kg/m}^2$ ($-2.7 \pm 1.3\%$; $P=0.02$) and was similar among patients taking or not taking valproate. Five patients stopped treatment before 30 days due to side effects. The above nonclinical and clinical information on lorcaserin justifies the development of lorcaserin in Dravet.

The study design and duration of treatment was selected based on Guidelines for Industry on Clinical Evaluation of Antiepileptic Drugs (FDA, 1997) and is similar to the design of registration clinical studies of Epidiolex, drug approved for treatment of Dravet syndrome (Devinsky et al., 2017) and recently reported fenfluramine study in Dravet syndrome (Lagae et al., 2020). Sample size was estimated based on the percent reduction of convulsive seizures and standard deviation reported in fenfluramine study in Dravet syndrome (Lagae et al., 2020).

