9 INVESTIGATIONAL PLAN

9.1 Overall Study Design and Plan

This is a multicenter, multiple-dose, randomized, double-blind, placebo-controlled, parallel-group adjunctive therapy study in subjects with Dravet syndrome. The study will consist of a Core Study and open-label Extension Phase.

The Core Study will include a Prerandomization and a Randomization Phase.

The Prerandomization Phase will include a Screening/Baseline Period (4 weeks), during which the subjects will be assessed for eligibility.

Once the Screening and Baseline procedures have been completed and eligibility has been established, the subjects will be randomized and begin treatment in the Randomization Phase. Approximately 58 subjects will be randomized to 1 of 2 treatment groups in a ratio of 1:1 and will receive lorcaserin or placebo for 14 weeks. The randomization will be stratified by previous treatment with fenfluramine (yes/no) and by weight categories (10 to <20 kg, 20 to <40 kg, and \geq 40 kg).

The Randomization Phase will consist of 2 periods: Treatment Period (14 weeks) and Follow-up Period (4 weeks).

During the Treatment Period, all subjects will take study drug twice daily (BID) based on weight as described in [Section 9.4.1](#).

For lower weight categories, during the first 2 weeks of Treatment Period, depending on the subject's clinical response and tolerability, the dose may be increased (not earlier than after 1 week of treatment) by 1 dose level at a visit. If the dose was increased, in the event of AEs, according to the investigator's clinical judgment, the dose may remain the same or can be decreased by 1 dose level, to the Target dose at any time during the Treatment Period. If the dose had been decreased, it may be increased again if tolerability improves.

All subjects who complete the Core Study will be eligible to enter the Extension Phase (refer to [Appendix 2](#)). The last visit of the Treatment Period of the Core Study is considered to be the 1st visit of the Extension Phase.

The Follow-up Visit will be conducted 4 weeks after the last dose of study drug for subjects who do not enter the Extension Phase.

An overview of the study design is presented in [Figure 1](#).

[figure not shown]

Figure 1 Study Design: E2023-A001-304 Core Study and Extension Phase

Follow-up can occur during the Randomization Phase (if the subject discontinued during the Randomization Phase), or during the Extension Phase, after the termination of study treatment.

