9.1.1 Prerandomization Phase

The Prerandomization Phase will last for 4 weeks and will include a Screening/Baseline Period, during which the subjects will be assessed for eligibility.

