9.3.1 Inclusion Criteria

Subjects must meet all of the following criteria to be included in this study:

1. Male or female, age ≥ 2 years at the time of informed consent (or assent)
2. Confirmed diagnosis of epilepsy with Dravet syndrome per Recommendations from a North American Consensus Panel (2017)
3. Has had at least 4 convulsive seizures during the 4 weeks of the Prerandomization Phase
4. Currently treated with at least 1 AED and the doses of all AEDs must be stable for at least 4 weeks before Screening, and be expected to remain stable throughout the study.
5. If vagal nerve stimulator, responsive neurostimulator, or deep brain stimulator is used, it must be implanted at least 5 months before Screening, parameters must be stable for at least 4 weeks before Screening, and be expected to remain stable throughout the study
6. If a ketogenic diet is followed, it must be stable for at least 4 weeks before Screening and be expected to remain stable throughout the study

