9.5.1.1 Screening Assessments

9.5.1.1.1 DEMOGRAPHY

Subject demography information will be collected at the Screening Visit. Demography information includes date of birth, sex, race/ethnicity.

Height and weight will be measured at the Screening Visit.

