9.5.1.4.5 VITAL SIGNS AND WEIGHT MEASUREMENTS

Vital sign measurements (ie, systolic and diastolic blood pressure [mmHg], pulse [beats per minute], respiratory rate [per minute], body temperature [in centigrade], and weight [kg]) will be obtained at the visits designated in the Schedule of Procedures/Assessments ([Table 3](#)) by a validated method. Blood pressure and pulse will be measured after the subject has been sitting for 5 minutes. All blood pressure measurements should be performed on the same arm, preferably by the same person.

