9.7.1.8 Safety Analyses

Safety analyses will be conducted on the Safety Analysis Set. The data will be summarized by overall, treatment group, and by age group.

The incidence of TEAEs, SAEs, AEs leading to discontinuation of study drug, and AEs leading to dose adjustment will be summarized. The incidence of TEAEs will be summarized by severity (mild, moderate, or severe), as well as by relationship to treatment (related or not related). Proportion of subjects with increased seizure frequency, weight and BMI changes will be summarized.

The change from baseline in vital signs and ECG parameters will be summarized, and changes from baseline in laboratory values will be summarized for continuous variables.

Incidence of FDA-defined valvulopathy and pulmonary hypertension, and change from baseline of echocardiographic parameters will be summarized. Incidence of bradycardia,

new onset heart block, new onset of other arrhythmias or conduction abnormalities, thickened valve leaflets, and restricted valve leaflet motion will be summarized.

Proportion of subjects with any treatment-emergent study-specific AEs will be summarized.

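### BMI change is to be summarised although height is scheduled only at Screening, so it would apparently repeat weight change and overstate BMI in children who grow

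*SAP*

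**What the plan says.** The safety analysis sections of both documents include a BMI summary. SAP section 5.6 lists "Proportion of subjects with increased seizure frequency, weight and BMI changes", and Protocol section 9.7.1.8 states "Proportion of subjects with increased seizure frequency, weight and BMI changes will be summarized". Neither defines how BMI is calculated, which height applies after baseline, or what counts as a BMI change.

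On measurement, Protocol section 9.5.1.1.1 states "Height and weight will be measured at the Screening Visit". Protocol Table 3 marks height at Visit 1 only. The vital-signs list in Protocol section 9.5.1.4.5 includes weight but not height. Table 4, the Extension schedule, has no height row. Weight is marked at every treatment visit in both tables.

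Subjects are eligible from age 2 with no upper age limit (Protocol section 9.3.1), so the population can include growing children and adults. SAP section 7 cuts back the efficacy, subgroup, sensitivity and PK analyses after the decision to terminate, but does not remove the BMI summary.

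**The concern.** BMI is meant to relate weight to current stature. If stature is frozen at its Screening value, the BMI summary carries no information beyond weight, and in a growing child it drifts upward for reasons unrelated to adiposity.

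The direction matters for this drug. Protocol section 7.1 records that lorcaserin was approved for chronic weight management. Protocol section 7.2 cites a case series with decreased appetite and weight loss among the common adverse events, and reports that "The mean decline in body mass index (BMI) at last follow-up compared to baseline was" 0.58 kg/m² (2.7%). A child who gains too little weight for the height gained could appear to have a stable or rising BMI. The Extension is the most exposed: every subject receives lorcaserin, there is no concurrent control, and SAP section 5.9 runs the safety analyses over the Core Study and Extension together, so the interval since the Screening height is longest.

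**Working it through.** **Figures in the documents.** The plan gives no figure for this artefact. The cited decline of 0.58 kg/m², or 2.7%, is a literature result that cannot be re-derived here. Together the two numbers imply a mean BMI of about 0.58 / 0.027 = 21.5 kg/m².

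**Interval.** For the pre-treatment interval, Protocol section 9.1.1 states "The Prerandomization Phase will last for 4 weeks". Core treatment lasts 14 weeks and Extension treatment 12 weeks. SAP section 8.2 sets the safety baseline before the date of randomization, so the scheduled baseline weight is also from Visit 1. Growth since the Screening height therefore accrues over up to 4 + 14 = 18 weeks at Week 14, and up to 4 + 14 + 12 = 30 weeks at Week 26.

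**Duplication.** Let W0 and H be weight and height at Screening, and Wt the later weight. With H fixed:

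percent BMI change = 100 × [(Wt/H²) / (W0/H²) − 1] = 100 × (Wt/W0 − 1) = percent weight change.

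Height cancels. This holds for every subject, whatever the height or growth.

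**Overstatement.** If the subject has grown by g, true BMI is Wt/(H + g)², so

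computed BMI / true BMI = (1 + g/H)², with g = v × weeks/52 for growth velocity v.

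The ratio exceeds 1 for any growth and equals 1 for none.

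**Size, under assumptions not in the documents** (v = 5 to 7 cm/year, H = 100 to 140 cm):

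| Interval | v = 5, H = 140 | v = 7, H = 100 |
|---|---|---|
| 18 weeks | g = 1.73 cm; (1 + 1.73/140)² − 1 = 2.5% | g = 2.42 cm; (1 + 2.42/100)² − 1 = 4.9% |
| 30 weeks | g = 2.88 cm; (1 + 2.88/140)² − 1 = 4.2% | g = 4.04 cm; (1 + 4.04/100)² − 1 = 8.2% |

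Outside that range, at 18 weeks: 85 cm and 8 cm/year gives 6.6%; 160 cm and 2 cm/year gives 0.9%; no growth gives 0%.

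**Against the 2.7% yardstick.** The growth that alone produces a 2.7% overstatement over 18 weeks is v = (√1.027 − 1) × H × 52/18. That is 3.87 cm/year at 100 cm, 4.65 at 120 cm, 5.42 at 140 cm and 6.20 at 160 cm. To illustrate, a true BMI fall of 2.7% at 18 weeks would be computed as 0.973 × 1.025 − 1 = −0.3% at the low end of the assumed range, and as 0.973 × 1.049 − 1 = +2.1% at the high end.

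**The case against.** The strongest reply is that weight is reported directly. Protocol section 9.7.1.8.4 and SAP section 5.6.4 summarise weight and its change by visit and treatment group, so an actual loss of weight will be seen. That stands. A reader might infer that the plan would miss weight loss on lorcaserin; it would not. What fixed-height BMI can mask is narrower: weight gain that falls short of linear growth.

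A second reply is that use of the Screening height is an inference. No formula is given, SAP section 9 places derivation rules in separate documents, and the protocol supplied (Version 2.0, July 2020) predates the SAP (Version 4.0, May 2024), so a later schedule may exist. This also stands, and is why the conclusion says apparently. On the schedule as supplied, however, no other height is available.

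A third is that the artefact should largely cancel between randomised arms if growth is similar. That is right for the Core contrast. It does not help within-arm change, the overall summary, subject-level proportions or the Extension.

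A reader might also infer that the artefact is about as large as lorcaserin's known BMI effect. The documents do not support that. They contain no growth rates or height distribution, and the 2.7% comes from a retrospective series of mixed epilepsy syndromes at last follow-up, with a median treatment duration of 10.8 months.

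**Conclusion.** The point holds in a limited form. On the schedule as supplied, BMI change would apparently rest on one height per subject. Percent BMI change is then identical to percent weight change, and later BMI is overstated in anyone who has grown. Those two results need no assumption beyond use of the Screening height.

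The size does need assumptions. At 5 to 7 cm/year and 100 to 140 cm it is about 2.5 to 4.9% at Week 14 and 4.2 to 8.2% at Week 26. It is smaller in slow-growing adolescents and zero in adults who have stopped growing. The cited 2.7% serves only as a rough yardstick: under these assumptions the artefact is not negligible beside it, and no closer comparison is warranted.

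The consequence is confined to a descriptive safety summary with no hypothesis or threshold attached, in a study being terminated with 22 subjects randomized. It is a minor correction, but the summary as planned would mislead for growing children.

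**What to change.** State in the SAP which height enters BMI, and compute BMI change only where a height was recorded at the same visit. For any subject still to be seen, add height at Visit 8, Visit 13 and the Early Discontinuation visits of both phases, where weight and physical examination are already scheduled.

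Heights not taken from subjects who have finished cannot be recovered. For those who were still growing, drop BMI change and report percent weight change and change in weight-for-age z-score. Age, sex and serial weights are already collected. The SAP should name the growth reference: the protocol cites CDC growth data only to justify the 10 kg lower weight limit, and the SAP plans regions outside the US. BMI change can stay for adults who have stopped growing, with a note that it repeats weight change.

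The cost is one brief measurement per added visit, or one derived variable. The limitation is that a weight-for-age z-score does not separate linear growth from adiposity, so it replaces a misleading summary without recovering true BMI.
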